6.1 Intent-to-treat Population

The intent-to-treat (ITT) population will include all randomized subjects. Subjects will be included in the treatment group to which they are randomized. Efficacy analyses will be performed based on the ITT population, unless otherwise specified.

6.2 Safety Analysis Population

The safety analysis population will include all randomized subjects who received at least 1 dose of IP. The analysis of safety data will be based on the safety population. Subjects will be included in the treatment group corresponding to the IP they actually received (apremilast or placebo). Subjects who inadvertently received more than 1 type or dose of IP in the placebo-controlled period will be analyzed according to their actual treatment received, where subjects who received \geq 1 dose of apremilast will be analyzed in the apremilast treatment group regardless of the randomized treatment. Safety analyses for the apremilast-exposure period will be based on the apremilast subjects as treated population, which includes all subjects who actually receive the apremilast 30 mg BID at the randomization or switched to the apremilast 30 mg BID at the week 16 visit.

6.3 Study-specific Analysis Sets

Not applicable.

7. Planned Analyses

7.1 Interim Analysis and Early Stopping Guidelines

No interim analysis will be conducted prior to the primary analysis.

7.2 Primary Analysis

The primary analysis will be performed after all subjects have either completed week 16 or discontinued the study.

7.3 Supplemental Analysis

After all subjects have either completed week 24 (visit 10) or discontinued the study, a supplemental analysis will be conducted. Statistical comparisons of treatment

differences will not be performed for this supplemental analysis. All analyses for placebo-controlled period in PA will not be repeated.

7.4 Final Analysis

Final analysis will be conducted based on all study data collected after all subjects have either completed or discontinued the study. In FA, the descriptive analyses at SA will be updated using the data from the final database lock. All analyses for placebo-controlled period in PA will not be repeated.

8. Data Screening and Acceptance

8.1 General Principles

The objective of the data screening is to assess the quantity, quality, and statistical characteristics of the data relative to the requirements of the planned analyses.

8.2 Data Handling and Electronic Transfer of Data

The Amgen Global Study Operations-Data Management (GSO-DM) department will provide all data to be used in the planned analyses including data from RAVE database, Clinical Outcome Assessment (COA), Patient-reported Outcome (PRO), and laboratory data (outside of RAVE database). The database will be subjected to edit checks outlined in the Data Management Plan (DMP). Additional details will be provided in DMP and Data Acquisition Requirements Specifications (DARS).

8.3 Handling of Missing and Incomplete Data

Subjects may have missing specific data points for a variety of reasons. In general, data may be missing due to a subject's early withdrawal from study, a missed visit, or inability to evaluate an endpoint at a particular point in time. The general procedures outlined below describe what will be done when a data point is missing.

8.3.1 Missing Baseline

Missing at baseline evaluations will not be imputed.

8.3.2 Missing Post-Baseline Evaluation

In the primary endpoint analysis of PPPASI-50 response at week 16, the PPPASI-50 values will be imputed as non-responder for visits on and after a subject experiencing any of the IEs. The missing PPPASI-50 values due to other reasons will be imputed using MI method.

For the secondary endpoints (i.e., the change from baseline at week 16 in PPPASI total score, PPSI total score, subject's VAS assessment for PPP symptoms [pruritus and pain/discomfort], and DLQI total score), the corresponding endpoints' baseline value will

be assigned to the data on and after any of the IEs regardless of the observed data and no imputation will be applied to the missing data (PPPASI total score) due to other reasons. Similar approach will be applied to the other endpoints of responses and continuous variables, unless otherwise specified.

For safety data, missing post-baseline measurements/assessments will not be imputed.

8.3.3 Missing and Incomplete Dates

For any listings, missing or incomplete dates will be listed as is.

The handling of incomplete and partial dates for safety, medical history and concomitant/prior medication/procedures will be described in Appendix C.

8.4 Detection of Bias

This study has been designed to minimize potential bias using randomization of subjects into treatment groups and the use of blinding. Other factors that may bias the results of the study include:

- major protocol deviations likely to impact the analysis and interpretation of the efficacy endpoints
- subject level unblinding before the final database lock and formal unblinding
- IP dosing non-compliance
- reasons for early withdrawal from treatment or from study

Important protocol deviations likely to impact the analysis and interpretation of the efficacy endpoints, and would significantly affect subject's right, safety or wellbeing will be tabulated by treatment group in the Clinical Study Report (CSR). Any unblinding of individual subjects prior to formal unblinding of the study will be documented in the CSR.

8.5 Outliers

Descriptive summaries will be examined to identify unexpected values.

Outliers that are not due to data entry will be included in the analysis. If it is deemed necessary after the team reviews the output from the planned analyses after database snapshot, a post-hoc sensitivity analysis excluding subjects with outliers may be performed.

8.6 Distributional Characteristics

For categorical endpoints, descriptive summary will be provided. For continuous endpoints, normality will be assumed given the large sample size where central limit theorem applies.

8.7 Validation of Statistical Analyses

Programs will be developed and maintained and output will be verified in accordance with current risk-based quality control procedures.

Tables, figures, and listings will be produced with validated standard macro programs where standard macros can produce the specified outputs.

The production environment for statistical analyses consists of Amgen-supported versions of statistical analysis software; for example, the SAS System version 9.4 or higher.

9. Statistical Methods of Analysis

9.1 General Considerations

The ITT principle will be used in statistical analyses for efficacy endpoints. For the placebo-controlled period (Weeks 0-16), efficacy evaluations will be conducted using the ITT population defined as all randomized subjects. Statistical comparisons for placebo-controlled period in Primary Analysis (PA) will be made between the two treatment groups (placebo and apremilast 30 mg BID). For the active treatment period (Weeks 16-52), analysis for differences between the two groups will not be performed although summaries of each group will be provided.

Descriptive statistics will be presented for appropriate endpoints at specified time points. Specifically, summary statistics for continuous variables will include the number of subjects (n), mean, SD, median, the 25th (Q1) and 75th (Q3) percentiles, minimum, and maximum. For efficacy variables, standard errors (SEs) for estimates will be included, unless otherwise specified. Frequency summary for categorical variables includes counts and percentages.

Statistical inferences will be provided for analyses of primary, secondary and the exploratory efficacy endpoints. Unless specified otherwise, all statistical tests are 2-sided with a significance level of 0.05; no statistical inference and imputation will be conducted for analyses of safety endpoints.

9.2 Subject Accountability

Frequency summary of subjects randomized, screened but not randomized among all screened subjects will be provided. The frequency of subjects who failed each inclusion/exclusion criteria will be included in the summary.

The number and percentage of subjects included in the ITT and safety analysis population will be summarized.

Subject disposition will be provided for placebo-controlled period and active treatment period based on ITT population respectively. Summary of safety follow-up period and study completion will be included in each disposition summary. The summaries include the number and percentage of subjects who entered the period, who completed the period, who completed IP, who ended IP and study with the reason. Subjects who ended IP are considered to enter the safety follow-up period unless the subjects ended the study on the same day.

Key study dates for the first subject screened and enrolled (randomized), last subject enrolled (randomized), data cut-off (last subject's week 16 and 24 visit), last subject end of IP, last subject end of study will be presented.

The number and percentage of subjects randomized will be tabulated by study site.

Listings of subject accountability will be provided.

9.3 Important Protocol Deviations

Important Protocol Deviations (IPDs) categories are defined by the study team before the first subject's initial visit and updated during the IPD reviews throughout the study. These definitions of IPD categories, subcategory codes, and descriptions will be used during the course of the study.

The number and percentage of subjects with at least one IPD will be summarized by each category in a table. The number of subjects reporting IPD and PD related to COVID-19 will be separately summarized. A by-subject listing of IPD will be provided. A COVID-19 related **PD** listing will also be provided.

9.4 Demographic and Baseline Characteristics

Summaries for the demographics, baseline characteristics, medical history, prior medication/procedure will be presented for the ITT population by treatment group and overall. Concomitant procedures/medications will be summarized based on the safety population.

Individual subject listings will be provided to support the summary tables.

9.4.1 Demographics

Summary statistics will be provided for the following continuous variables:

- Age
- Weight
- Height
- BMI (Weight [kg]/Height [m²])

Number and percentage of subjects will be provided for the following categorical variables:

- Age (< 40, ≥ 40 to < 65, ≥ 65 years)
- Sex (male, female)
- Ethnicity (Hispanic or Latino, Not Hispanic or Latino)
- Race (American Indian or Alaska Native, Asian, Black or African American, Native Hawaiian or Other Pacific Islanders, White, Other). If multiple races have been reported for a subject, the subject will be categorized as multiple-race, as well as by combination of races.
- BMI category (< 25, ≥ 25 to < 30, ≥ 30 kg/m²)

9.4.2 Baseline Disease Characteristics

Summary statistics will be provided for the following continuous variables:

- Duration of PPP in years
- PPPASI total score
- PPSI total score
- VAS for PPP symptoms (pruritus and pain/discomfort)
- DLQI total score

Number and percentage of subjects will be provided for the following categorical variables:

- Tobacco Use (Current/Past User, Non-User)
- Duration of PPP (< 2, \geq 2 to < 6, \geq 6 to < 10, \geq 10 years)
- PPPASI total score rounded range (clinical and IRT data) ($\leq 20, \geq 21$ to $\leq 30, \geq 31$)
- Presence of focal infection (clinical and IRT data) (Yes, No)
- Presence of pustulotic arthro-osteitis (PAO) (Yes, No)
- Presence of nail lesion (Yes, No)
- Prior use of biologic DMARDs for PPP (Yes, No)
- History of focal infection including periodontitis, tonsilitis and sinusitis (Yes, No)

9.4.3 Medical History

Medical history terms will be coded using the Medical Dictionary for Regulatory Activities (MedDRA) version 24.0 or higher. A frequency summary (counts and percentage of subjects) of medical history will be presented by system organ class (SOC) and preferred term (PT). A similar table summarizing currently active medical histories that were not resolved/recovered by randomization will be provided. Medical history summaries of focal infection and PAO will be provided. Individual subject listings of medical history will be provided.

9.4.4 Prior and Concomitant Procedures

Prior procedures are defined as those started before Study Day 1 (whether or not ended before Study Day 1). Concomitant procedures are defined as procedures that were either initiated before Study Day 1 and continued during the study treatment, or initiated on/after the date of Study Day 1 and on/before the date of treatment discontinuation. Procedures initiated prior to the start of study treatment and were continued after the start of study treatment will be counted as both prior and concomitant procedures.

Frequency summaries of prior and concomitant procedures will be provided by verbatim term, and location.

A subject listing of prior and concomitant procedures will be provided.

9.4.5 Prior and Concomitant Medications

Prior and concomitant medications are defined similarly as prior and concomitant procedures, respectively.

Number and proportion of subjects receiving prior/concomitant medications will be summarized by preferred term or category for each treatment group as coded by the World Health Organization Drug dictionary. The prior **and concomitant** medications for PPP, focal infection and PAO will be summarized separately.

A subject listing of prior and concomitant medications will be provided.

9.5 Efficacy Analyses

The efficacy analyses will be performed based on the ITT population.

To control the overall type I error at the level of 0.05 (2-sided), a fixed-sequence testing procedure will be applied. The secondary efficacy endpoints will be tested with the listed order in Section 9.5.2 if the primary endpoint achieves statistical significance.

Sensitivity analyses will be performed for the primary estimand.

Subject data listings of efficacy data will be provided.

9.5.1 Analyses of Primary Efficacy Endpoint(s)/Estimand(s)

The primary efficacy endpoint is the achievement of PPPASI-50 response at week 16. The proportion of subjects achieving PPPASI-50 response in apremilast 30 mg BID group and placebo group will be compared using Cochran-Mantel-Haenszel (CMH) test adjusting for the stratification factors for randomization [PPPASI total score range ($\leq 20 / 21-30 / \geq 31$) at baseline and subject's focal infection status (yes/no) at baseline]. The testing will be conducted at the 2-sided 0.05 significance level. Subjects who discontinue IP prior to week 16 due to lack of efficacy, adverse event, or use of protocol prohibited medication will be considered as treatment failures as the result of the IE and the PPPASI-50 values for visits on and after the IE will be imputed as non-responders. The missing data (PPPASI total score) due to other reasons will be imputed using MI method.

The two-sided p-values from the CMH test, the adjusted treatment difference in proportion using the weighted average of the treatment differences across the strata with the CMH weights, along with the associated two-sided 95% CIs using a normal approximation to the weighted average will be provided. Similarly, unadjusted treatment differences in proportions will also be provided.

Sensitivity analyses for the primary endpoint will be conducted using the non-responder imputation (NRI) method for any missing data **due to other reasons (not IE)**. Additionally, to assess sensitivity to departures from the missing data assumption (MAR), the tipping point analysis will be performed. Another sensitivity analysis for the primary endpoint will be performed based on data-derived stratification factors.

For MI method, the SAS procedure MI will be used to impute missing PPPASI scores at the scheduled analysis visits in the Placebo-controlled Phase (Week 0-16) to create M=50 complete datasets. The missing data patterns will be checked at the scheduled

analysis visits, i.e., Baseline (week 0), week, 2, 4, 6, 8, 12, and 16. If there are nonmonotone missing patterns, two separate imputation procedures will be used to complete the imputation process.

- In the first step, the Markov Chain Monte Carlo (MCMC) method will be used to impute missing scores by treatment and stratification factor to create M=50 imputed data sets with monotone missing patterns. The minimum and maximum values for imputation will correspond to the lowest and the highest scores. The seed will be set to 17813722, a single chain will be used to produce imputations. In case there are convergence issues, a simple model will be used to impute the missing scores by treatment, with further simplification by dropping both treatment and stratification factor in imputation model if necessary.
- In the second step, the predictive mean matching method will be used to impute the remaining missing values for the 50 data sets with monotone missing patterns. The MONOTONE REGPMM statement will be used with seed 55218164. The missing values at each visit will be imputed based on treatment, stratification factor and previous visits. The number of closest observations to be used in the selection will be K=2.

After the completion of imputation, the same analysis method/model will be used to analyze the 50 complete data sets and the SAS procedure MIANALYZE will be used to combine the results for the statistical inferences.

Endpoint/Estimand	Primary Summary and Analysis Method	Sensitivity Analysis
Achieving PPPASI- 50 response at week 16	The treatment failures will be considered as non-responders on and after the IE and the missing value (PPPASI total score) due to other reasons will be imputed using MI method. The two-sided p-values from the CMH test, the adjusted treatment difference in proportion using the weighted average of the treatment differences across the strata with the CMH weights, along with the associated two-sided 95% CIs using a normal approximation to the weighted average will be provided. Similarly, unadjusted treatment differences in proportions will also be provided.	 Tipping point analysis to assess sensitivity to departures from the missing data assumption (MAR) NRI for any missing data Adjusting for the data- derived stratification factors instead of the factor from IRT

Table 9-1. Primary Efficacy Endpoint Summary Table

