The sample size estimation is based on the results of the phase 2 study (CC-10004-PPP-001 [20200055]). Assuming that a proportion of subjects achieve PPPASI-50 response of 40% and 65% at week 16 for the placebo group and the apremilast 30 mg BID group, respectively, a sample size of approximately 170 subjects in total (85 subjects per group) provides 90% power using a chi-square test with a 2-sided alpha of 0.05. A dropout rate of 5% is anticipated during the double-blind placebo-controlled period of the study.

Planned Analyses

The primary analysis will be performed after all subjects have completed the week 16 visit (visit 8) or have been discontinued from the study. An additional analysis will be conducted after all subjects have completed the week 24 visit (visit 10) or have been discontinued from the study. At the end of the study, after all subjects have either completed the study or been discontinued, the final analysis will be performed. The efficacy analyses will be performed on the ITT population.

The primary endpoint is the achievement of PPPASI-50 at week 16. Subjects who discontinued treatment prior to week 16 (due to lack of efficacy, an adverse event, or protocol deviation due to prohibited medication usage) will be considered as treatment failures and non-responders in the primary analysis. Missing values of the data in which the treatment failures are considered as non-responders will be imputed using multiple imputation (MI).

The treatment difference between the apremilast 30 mg BID group and the placebo group will be analyzed using the Cochran–Mantel–Haenszel (CMH) test, adjusting for the stratification factor at randomization. The 2-sided p-value from the CMH test, the adjusted treatment difference in proportion using the weighted average of the treatment

Protocol Number: 20200195

Date: 15 April 2022 Page 14 of 99

differences across the strata, and the associated 2-sided 95% CI will be provided. The statistical test will be 2-sided at the significance level of alpha = 0.05.

Secondary efficacy endpoints, such as the PPPASI total score change from baseline at week 16, will be analyzed using the mixed-effect model for repeated measures (MMRM) with treatment group, visit time, treatment-by-time interaction, and stratification factors as fixed effects, and the baseline value as a covariate.

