6.1.4 Excluded Treatments and/or Procedures During Study Period

Table 6-2. Excluded Treatments and/or Procedures During Study Period

Prohibited Treatment	Time Period for Exclusion
Strong cytochrome P450 3A4 (CYP3A4) enzyme inducers (eg, rifampin, phenobarbital, carbamazepine, phenytoin and St. John's Wort)	2 weeks or 5 times the half-life, whichever duration is longer, prior to randomization and until the end of active treatment
Granulocyte and monocyte adsorption apheresis	2 weeks prior to randomization until the end of active treatment
Topical therapies that could affect PPP or the efficacy evaluation (including, but not limited to, corticosteroids, retinoid, vitamin D3 derivatives, tacrolimus, antihistamine, antibiotics or traditional Chinese/Japanese herbal preparations).	2 weeks prior to randomization and during double-blind, placebo-controlled period; allowed after week 16 Note: Only use of topical antibiotics for the treatment after skin biopsy is permitted. Unmedicated skin moisturizer (eg, Vaseline) will be permitted as needed.
Conventional systemic therapies that could affect PPP or the efficacy evaluation (including, but not limited to corticosteroids, antihistamine, antibiotics, JAK inhibitors, 1,25-dihydroxy vitamin D3 and analogues, psoralens, sulfasalazine, hydroxyurea, dimethyl fumarate, biotin, or colchicine)	4 weeks prior to randomization until end of active treatment Note: Systemic antihistamines are allowed after week 16
Systemic therapy for PAO including, but not limited to bisphosphonates,	4 weeks prior to randomization and until end of active drug treatment period

Protocol Number: 20200195

Date: 15 April 2022 Page 36 of 99

immunosuppressants [eg, MTX, azathioprine, cyclosporine or 6-thioguanine, mercaptopurine, mycophenolate mofetil, tacrolimus]) and other biologics (eg, anti-IL1 antibody)

Note: Background stable doses of NSAIDs for treatment of PAO are permitted.

Page 1 of 2

Protocol Number: 20200195

Date: 15 April 2022 Page 37 of 99

Table 6-2. Excluded Treatments and/or Procedures During Study Period

Prohibited Treatment	Time Period of Exclusion	
Prolonged sun exposure or used tanning booths or other ultraviolet light sources	4 weeks prior to randomization and until the end of active treatment period	
Biologic therapy such as:		

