6.6.2 Concomitant Treatment

Throughout the study, investigators may prescribe any concomitant medications or treatments deemed necessary to provide adequate supportive care except for those listed in Section 6.1.4.

Concomitant therapies are to be collected from day 1 through the **30**-day post-treatment safety follow-up. For all other concomitant therapies, collect therapy name, indication, dose, unit, frequency, route, start date, and stop date.

Protocol Number: 20200195

Date: 15 April 2022 Page 40 of 99

7. Discontinuation of Study Treatment and Subject Discontinuation/Withdrawal

Subjects have the right to withdraw from investigational product and/or other protocol-required therapies, protocol procedures, or the study as a whole at any time and for any reason without prejudice to their future medical care by the physician or at the institution.

The investigator and/or sponsor can decide to withdraw a subject(s) from investigational product, device, and/or other protocol-required therapies, protocol procedures, or the study as a whole at any time prior to study completion for the reasons listed in Section 7.

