7.1 Discontinuation of Study Treatment

Subjects (or a legally authorized representative) can decline to continue receiving investigational product and/or other protocol-required therapies and/or procedures at any time during the study but continue participation in the study. If this occurs, the investigator is to discuss with the subject the appropriate processes for discontinuation from investigational product or other protocol-required therapies and must discuss with the subject the possibilities for continuation of the Schedule of Activities (see Table 1-1) including different options of follow-up (eg, in person, by phone/mail, through family/friends, in correspondence/communication with other treating physicians, from the review of medical records) and collection of data, including endpoints, adverse events, and must document this decision in the subject's medical records. Subjects who have discontinued investigational product and/or other protocol-required therapies and/or procedures should not be automatically removed from the study. Whenever safe and feasible, it is imperative that subjects remain on-study to ensure safety surveillance and/or collection of outcome data.

Reasons for early removal from protocol-required investigational product(s) or procedural assessments may include any of the following:

- decision by Sponsor
- lost to follow-up
- death
- adverse event
- subject request
- lack of efficacy
- protocol deviation
- pregnancy

Protocol Number: 20200195

Date: 15 April 2022 Page 41 of 99

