To control the overall Type I error rate at the 0.05 level (2-sided) for comparisons between the apremilast 30 mg BID group and the placebo group, a fixed-sequence testing procedure will be applied for efficacy endpoints. Secondary efficacy endpoints will be statistically tested in the order following order (change from baseline at week 16) if the primary analysis result is statistically significant:

- 1. PPPASI total score
- 2. PPSI total score
- 3. Subject's VAS assessment for PPP symptoms (pruritus)

Protocol Number: 20200195

Date: 15 April 2022 Page 56 of 99

	Subject's VAS assessment for PPP symptoms (pain/discomfort)	
	5. DLQI total score	
	Further sequence will be prespecified in the SAP prior to the week 16	
	database lock.	
Exploratory	Will be described in the SAP finalized before the database lock for the	
	primary endpoint.	

Additional estimand(s) providing additional treatment efficacy insight will be included in the SAP.

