2.1 Objectives and Endpoints/Estimands

Objec	tives	Endpoints			
Prima	Primary				
•	To evaluate the efficacy of apremilast 30 mg twice daily (BID) compared with placebo in subjects with PPP	 Achieving at least 50% reduction from baseline in Palmoplantar Pustulosis Area and Severity Index (PPPASI) total score (PPPASI-50) at week 16 			
Seco	ndary				
•	To evaluate the efficacy of apremilast 30 mg BID compared with placebo in subjects with PPP	 Change from baseline in PPPASI total score at week 16 Change from baseline in Palmoplantar Pustulosis Severity Index (PPSI) total score at week 16 Change from baseline in subject's Visual Analogue Scale (VAS) assessment for PPP symptoms (pruritus and pain/discomfort) at week 16 Change from Baseline in Dermatology Life Quality Index 			
		(DLQI) total score at week 16			
•	To evaluate the safety and tolerability of apremilast 30 mg BID compared with placebo in subjects with PPP	 Treatment-emergent adverse events (TEAEs), serious TEAEs, and TEAEs of interest Clinically significant changes in body weight, vital signs, and laboratory abnormalities 			

Primary Estimand

The main estimand of primary interest for the primary efficacy endpoint (i.e., achievement of PPPASI-50 response defined as at least 50% reduction from baseline in PPPASI total score, at week 16) is defined in terms of the following attributes:

- The target population of interest is Japanese subjects with PPP defined through the inclusion/exclusion criteria.
- The primary endpoint is the achievement of PPPASI-50 response at week 16.
- Intercurrent events (IEs) are investigational product (IP) discontinuation due to lack of efficacy, adverse event, or protocol-prohibited medication use. A subject will be considered a treatment failure after any of the IEs.
- The summary measure is the difference between apremilast 30 mg BID group and placebo group in proportion of responders based on the intent-to-treat (ITT) population including all randomized subjects.

A missing value after any of the IEs will be imputed as non-responders, otherwise, will be imputed with a multiple imputation (MI) method. A non-missing value after any of the IEs will also be imputed as non-responders.

Secondary Estimand(s)

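### Does the primary analysis need an explicit rule, or an extra analysis, for subjects who use a prohibited therapy but stay on IP?

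*SAP*

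**What the plan says.** SAP 2.1 defines the events in a single bullet: "Intercurrent events (IEs) are investigational product (IP) discontinuation due to lack of efficacy, adverse event, or protocol-prohibited medication use". SAP 9.5.1 applies the definition to "Subjects who discontinue IP prior to week 16 due to lack of efficacy, adverse event, or use of protocol prohibited medication" and scores their PPPASI-50 values as non-response from the event onward. The protocol synopsis uses the same construction: "Subjects who discontinued treatment prior to week 16 (due to lack of efficacy, an adverse event, or protocol deviation due to prohibited medication usage". SAP 9.5.2 repeats it for the secondary endpoints, with the baseline value assigned instead.

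SAP 8.3.2 and 9.5.1 replace two kinds of primary-endpoint value: those on and after an intercurrent event, and those missing for other reasons, which go to multiple imputation. SAP 9.1 places the efficacy analyses under the ITT principle.

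The prohibited list in Protocol 6.1.4 (Table 6-2) includes "Topical therapies that could affect PPP or the efficacy evaluation" and "Conventional systemic therapies that could affect PPP or the efficacy evaluation". Protocol 7.1 introduces its list with "Reasons for early removal from protocol-required investigational product(s) or procedural assessments may include any of the following"; protocol deviation, adverse event and lack of efficacy are all on it.

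The primary sensitivity analyses in SAP 9.5.1 and Table 9-1 are non-responder imputation of missing data, a tipping-point analysis, and data-derived strata. Table 9-2 plans none for the secondary endpoints. Protocol 9.4.2.2 adds: "Additional estimand(s) providing additional treatment efficacy insight will be included in the SAP".

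**The concern.** Two subjects with the same prohibited exposure can be scored differently. If IP is stopped because of it, the subject is a non-responder. If IP continues, a good week-16 score counts as a response, although the protocol itself describes these therapies as able to affect the disease or its assessment. Stopping is not mandatory after such use, so the score can turn on a decision at the site.

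The rule must also be inferred. The SAP 2.1 bullet, taken alone, could be read as making prohibited use an event in its own right, and a programmer working only from it might code differently from one working from SAP 9.5.1. None of the three listed sensitivity analyses alters an observed value, so they could not show whether the result depends on the rule. At stake is the PPPASI-50 difference, and through the fixed testing sequence, the five secondary tests behind it.

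**Working it through.** **Is the rule determinate?** There are three places to compare.

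- SAP 9.5.1 and 9.5.2: the grammatical subject is stopping IP; prohibited medication is a reason for it.
- Protocol synopsis: the three reasons stand in parentheses after discontinuation, so no second reading is available.
- SAP 2.1 bullet: two readings are possible in isolation. The analysis sections settle which applies. The corresponding bullets in Protocol 1.1, 3 and 9.4.2.2 each follow a sentence that names subjects who discontinue IP.

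A week-16 value that is present, with no event before it, belongs to neither replaced class. It is analysed as observed.

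**The plan's own figure.** SAP 3.2 assumes 40% and 65% response, 85 per arm, chi-square test, two-sided 0.05. With mean rate 0.525:

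- power = Φ{[0.25 × √85 − 1.96 × √(2 × 0.525 × 0.475)] / √(0.40 × 0.60 + 0.65 × 0.35)}
- = Φ{(2.305 − 1.384) / 0.684} = Φ(1.347) = 91.1%

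The exact binomial value is 91.7%. With 81 per arm (85 less 5%) the formula gives 89.7%. The stated 90% reproduces. If 40% and 65% are the rates under the rule as written, the rule costs the primary test no power.

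**How many reclassifications would matter?** The test is an uncorrected, unstratified chi-square, z = (difference in proportions) / √[p̄(1 − p̄) × 2/85], where p̄ is the pooled proportion. Each reclassified responder moves the difference by 1/85 = 1.18 points. The counts nearest plan are 34 (placebo) and 55 (apremilast): p̄ = 89/170 = 0.5235, difference 21/85 = 24.7 points, z = 3.22, p = 0.0013.

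| Responders reclassified (placebo / apremilast) | Counts | Difference, points | p |
|---|---|---|---|
| 0 / 3 | 34 v 52 | 21.2 | 0.0058 |
| 0 / 5 | 34 v 50 | 18.8 | 0.014 |
| 0 / 8 | 34 v 47 | 15.3 | 0.046 |
| 0 / 9 | 34 v 46 | 14.1 | 0.065 |
| 1 / 9 | 33 v 46 | 15.3 | 0.046 |
| 1 / 10 | 33 v 45 | 14.1 | 0.065 |
| 2 / 11 | 32 v 44 | 14.1 | 0.064 |

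Nine on apremilast and none on placebo is the smallest change that loses significance, though not the only one. Three in each arm leave 24.7 points. Three on placebo alone widen the gap to (55 − 31)/85 = 28.2 points.

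Weaker starting points are more fragile. From 34 v 50 (p = 0.014), four apremilast-only changes lose significance. From 34 v 48 (p = 0.032), two do. From 34 v 47 (p = 0.046), one does. In the other direction, 34 v 44 (p = 0.124) becomes 31 v 44 (p = 0.045) when three placebo responders change.

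**Which way would it push?** The documents give no use rates and no response rates among users. Assume 30% to 60% of users respond, and take the planned rate minus (use × response among users) as the rate with users counted as failures. Starting from 25 points:

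| Assumed use (placebo / apremilast) | Difference, points |
|---|---|
| 5% / 2% | 25.9 to 26.8 |
| 10% / 3% | 27.1 to 29.2 |
| 5% / 5% | 25.0 |
| 2% / 5% | 24.1 to 23.2 |
| 3% / 10% | 22.9 to 20.8 |

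For example, 5% / 2% with 30% response gives (0.65 − 0.006) − (0.40 − 0.015) = 0.259. Heavier use on placebo makes the plan's rule conservative, equal use with equal response leaves the difference alone, and heavier use on apremilast flatters it. The text does not indicate which applies.

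**The case for a change.** The strongest case for acting is that prohibited use on continued IP is foreseeable and the remedy looks cheap. Protocol 6.6.2 already asks sites to record what is needed ("For all other concomitant therapies, collect therapy name, indication, dose, unit, frequency, route, start date, and stop date"), so blinded review could flag such subjects and one supplementary table could count them as non-responders. Alpha, testing order and the primary estimate would stay as they are. A clear definition does not supply a robustness check, and deviation and medication tables count users without re-estimating the effect.

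This is fair, and part of it stands: no listed analysis addresses the point, and the rule is inferred. It does not amount to a defect in the plan.

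- Discretion over stopping applies equally to adverse events and lack of efficacy under Protocol 7.1, and those decisions are made while treatment is blinded (Protocol 6.3.2).
- The absence of such an analysis cannot be established. The protocol defers additional estimands to the SAP, and the SAP's exploratory tables are blank in the public copy. Those blanks do not prove that one exists either.
- The planned subject listings of concomitant medications and procedures, important deviations and efficacy data would let affected subjects be found and re-scored. Only prespecification would be missing.
- The cost is higher than it looks. Table 6-2 also bars phototherapy, apheresis and focal-infection procedures, so medication records alone would not be enough. Sun exposure and tanning are not evidently covered by the therapy fields. Aligning the protocol's bullets would need an amendment and ethics submission.

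**Conclusion.** No change follows. The gap is one that analysts fill sensibly from SAP 8.3.2, 9.5.1 and 9.5.2: the week-16 value of a subject who stays on IP is used as observed. That is an acceptable estimand choice. It yields no wrong number, no bias in a known direction and no loss of the planned power.

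A result near plan tolerates eight apremilast-only reclassifications out of 55 responders and is lost at nine. A result around 34 v 48 would tolerate only one. These counts assume 85 per arm, an unstratified chi-square test and no imputation; the use and response rates behind the scenario differences are assumptions. An explicit sentence or a supplementary analysis would help a reader, but the soundness of the primary result does not depend on either.
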